#### 3) Tipping point analysis:

This document is confidential.

SAP text Version: SAP text 3.0 6-Dec-2023

Controlled Document ID: 3903A.02, Effective Date 31-Aug-2020

In the event that statistical significance in favor of ecopipam is determined from the primary analysis, subjects in the ecopipam group with a missing YGTSS-TTS score (change from randomization) will be assigned successively more extreme values, whilst subjects in the placebo group with a missing YGTSS-TSS score (change from randomization) will be assigned successively less extreme values, to find the point at which statistical significance is lost (i.e. the 2-sided P-value becomes greater than 0.05 or significance is in favor of placebo).

Details for tipping point analysis are described below:

- a. For patients that completed the study, intermittent missing data are considered as MAR and will be imputed by predictive mean matching multiple imputation method (Heitjan and Little 1991, Schenker and Taylor 1996). The imputation model will include age group at baseline, region, treatment arm, week 12 TTS score, and TTS scores at all visits up to the imputed visit where the TTS is scheduled to be collected.
- b. For patients who discontinued due to any reason, all missing data will be imputed using the same predictive mean matching multiple imputation method. The imputed values will be adjusted under MNAR assumption:
  - o Patients randomized to ecopipam: the first missing value after patients dropout will be analyzed assuming the unobserved outcome is on average worsened by  $\delta$ 1 (where  $\delta$ 1 = 1 to 10 or estimated treatment effect (MAR model), whichever is higher, in step of 1) compared to the patients who have no missing value;
  - o Patients treated by placebo: the first missing value after patients dropout will be analyzed assuming the unobserved outcome is on average better by  $\delta 2$  (where  $\delta 2 = 1$  to 10 or estimated treatment effect (MAR model), whichever is higher, in step of 1) compared to the patients who have no missing value;

The penalty or reward will not be applied to the values from later time points as these values are penalized or rewarded through condition on previous time points. For each combination of  $(\delta 1, \delta 2)$ , 100 imputed datasets will be obtained.

c. The resulting complete, imputed datasets will each be analyzed using the same model as the primary analysis model, and the resulting statistics combined using methodology provided by Rubin (1987) and Little and Rubin (2002).

The complete multiple imputation methodology, along with SAS code, is detailed in Appendix (Section 16.4).

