During the R/WD period, subjects will return to the clinic every week for the first 4 weeks and every 2 weeks thereafter (Weeks 13, 14, 15, 16, 18, 20, 22 and 24) and efficacy and safety assessments will be conducted at each of these visits. Any subject meeting Relapse criteria, defined as the loss of  $\geq$  50% of the improvement experienced on the YGTSS-TTS from Baseline (Day 1) to the last visit of the open-label Stabilization period Week 12, or initiation of additional medications to treat symptoms of TD, or requirement of hospitalization for worsening symptoms of TD will be withdrawn from blinded study medication (ecopipam or placebo).

An interim analysis (IA) will be conducted by an independent data safety monitoring board (DSMB) after approximately 70% of Relapse events have accrued (34 Relapse events). For details, please refer to section 13.

Non-responders to ecopipam during the open-label Stabilization period at either Week 8 or Week 12, or Responders randomized to ecopipam who complete the R/WD period, or who meet Relapse criteria during the R/WD period, or any subjects who discontinue the study prematurely for any reason will be

This document is confidential.

SAP text Version: SAP text 3.0 6-Dec-2023

Controlled Document ID: 3903A.02, Effective Date 31-Aug-2020

tapered off ecopipam in decrements of 22.4-mg/day and will complete the Week 24/Relapse/ET visit. Subjects assigned to placebo will receive placebo taper down medication to preserve the blind.

Follow Up visits will be conducted in the clinic 7 and 14 days after the last dose of study medication. Subjects will also be contacted by telephone 30 days after the last dose of study medication to determine any adverse events, with the exception of subjects who roll into the open-label extension study EBS-101-TD-391 within 30 days of their last study drug.

Subjects who experience Relapse may be treated for their TD with medications recommended by the PI or referred back to their primary physician for treatment after completing Day 7 and 14 follow-up visits.

Responders to ecopipam who complete the R/WD period and who complete the Week 24/Relapse/ET visit and the Day 7 and 14 follow-up visits are eligible to enter into the long-term open-label study EBS-101-TD-391. Subjects who meet the criteria for Relapse and complete the Week 24/Relapse/ET visit and the Day 7 and 14 follow-up visits will have the opportunity to enter the long-term open-label study.

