# 4.3. Determination of Sample Size

The planned number of Relapse events for the double-blind R/WD Phase is 49 in children and adolescents. This number of events will provide 85% power to detect a difference between treatment groups, assuming a hazard ratio of 0.4 for Relapse and statistical testing at alpha level 0.05 (2-sided). Subject enrollment will stop around the time that 49 Relapse events among children and adolescents are anticipated to have occurred. The number of Relapse events among adults will not determine study completion.

Assuming the proportion of subjects who Relapse in the DB randomization phase is 65% in the placebo group and 34% in the ecopipam group, approximately 98 subjects (49 subjects per group) will be required to achieve this number of Relapse events.

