#### 8.4. Visit Windows

The following visit windows will be used in the summarization or analysis of data. If the subject's last non-missing data point falls within the window, even if additional data points fall within the window, then that last data point will be used. Else, if more than 1 data point falls within a window then the data point closest to the target day will be used. If there are 2 data points equidistant to the target day, one high and one low, then the high data point will be used. Visit windowing will not be applicable to follow-up visits. If a subject terminates the study early, all assessments collected at the Early Termination visit will be assigned to the next scheduled visit (per Schedule of Assessments for the parameter) where the assessment would have been collected.

If Baseline is Day 1, then:

Day 15 (target day = 15) 2 - 21 and no randomization

Week 4 (target day = 29) 22 - 42 and no randomization

Week 8 (target day = 57) 43 - 70 and no randomization

Week 12 (target day = 85) 71 and above with no randomization

Week 13 (target day = 92) 78 - 95 and randomized

Week 14 (target day = 99) 96 - 102 and randomized

Week 15 (target day = 106) 103 - 109 and randomized

Week 16 (target day = 113) 110 - 119 and randomized

Week 18 (target day = 127) 120 - 133 and randomized

Week 20 (target day = 141) 134 - 147 and randomized

Week 22 (target day = 155) 148 - 161 and randomized

Week 24 (target day = 169) 162 and above (randomized and not a follow-up visit)

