# 16.4. Tipping Point Analysis

Let delta1 and delta2 be the penalty to ecopipam group and reward for placebo group, respectively. Delta1 and delta2 = 1 to 10 (or estimated treatment effect from exploratory (mean change) analysis if it is larger than 10) in step of 1. General steps for this analysis includes:

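### The tipping-point grid starts both deltas at 1, so it cannot give an ecopipam-only tipping penalty; its lowest row puts that penalty roughly 1 to 2 points too low

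*SAP*

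**What the plan says.** SAP 10.2.25.1, item 3, applies if the analysis favours ecopipam. Imputed values for ecopipam dropouts are worsened by delta1 and those for placebo dropouts are improved by delta2. Each delta runs over "1 to 10 or estimated treatment effect (MAR model), whichever is higher, in step of 1". Significance counts as lost when "the 2-sided P-value becomes greater than 0.05 or significance is in favor of placebo". The shift is made once per subject, at the first missing value after dropout: "The penalty or reward will not be applied to the values from later time points", because later imputed values are conditioned on the shifted one.

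Appendix 16.4 repeats the scheme. "Let delta1 and delta2 be the penalty to ecopipam group and reward for placebo group, respectively", it says, and then "Delta1 and delta2 = 1 to 10". In the SAS code of Step 1, the outer loop (delta1) and the inner loop (delta2) both begin at 1 and end at 10.

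The same section has two other missing-data analyses. Item 1 is MAR multiple imputation. Item 2 is jump to reference, which imputes missing values from the placebo arm and gives placebo no reward.

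**The concern.** A tipping-point analysis should show how far from MAR the missing data must lie before the conclusion changes. The question most readers ask first is how much worse the ecopipam dropouts must have done, on their own, to overturn the result. That is the row delta2 = 0, and the grid does not contain it. Every combination mixes an ecopipam penalty with a placebo reward.

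Two things are lost. First, no ecopipam-only tipping value can be read off. Second, if significance holds under MAR but is gone at (1,1), no grid point lies on the significant side, and the boundary is known only to fall somewhere between the origin and (1,1).

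The design makes this more than a formality. Subjects who relapse are taken off blinded medication, and more are expected to relapse on placebo. A one-point placebo reward may therefore move the Week 24 difference further than a one-point ecopipam penalty.

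**Working it through.** **The grid.** Delta1 and delta2 each take 10 values, so there are 10 × 10 = 100 combinations. The smallest is (1,1), and none has delta1 = 0 or delta2 = 0. Raising the upper limit to the MAR effect, when that exceeds 10, does not change the starting point. With both deltas starting at 0 and an upper limit of 10 there are 11 × 11 = 121.

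**The rates used as a guide to missingness.** SAP 4.3 says: "Assuming the proportion of subjects who Relapse in the DB randomization phase is 65% in the placebo group and 34% in the ecopipam group". They agree with the planned event count: 49 × 0.65 + 49 × 0.34 = 31.85 + 16.66 = 48.5, about 49. They are assumptions for children and adolescents, whereas the mean-change model also includes adults. The documents give no missing-data rate for YGTSS-TTS and no rate of dropout for reasons other than relapse.

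**Shift in the Week 24 difference.** Let w_p and w_e be the fractions of placebo and ecopipam Week 24 scores that are missing, each multiplied by the share of delta that reaches Week 24. Then

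- shift = w_e × delta1 + w_p × delta2
- with slack = difference − 1.96 × SE, tipping delta1 = (slack − w_p × delta2) / w_e
- moving from delta2 = 0 to delta2 = 1 lowers the tipping delta1 by w_p / w_e.

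**Ratio with equal carry-through in both arms and a fixed SE.** Constant hazards are −ln(0.35)/12 = 0.0875 and −ln(0.66)/12 = 0.0346 per week. A relapse assessed at Week 24 itself leaves that score observed, so the cut-off is Week 22, ten weeks after randomization: 1 − 0.35^(10/12) = 58.3% and 1 − 0.66^(10/12) = 29.3%. SAP 8.4 also says that "all assessments collected at the Early Termination visit will be assigned to the next scheduled visit". If this moves a Week 22 relapser's score to Week 24, the cut-off becomes Week 20.

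| Assumed missing at Week 24 | Placebo | Ecopipam | Ratio (points) |
|---|---|---|---|
| Planned relapse rates as they stand | 65% | 34% | 1.91 |
| Relapse by Week 22, constant hazards | 58.3% | 29.3% | 1.99 |
| Relapse by Week 20, constant hazards | 50.3% | 24.2% | 2.08 |
| Planned rates, plus 10% of non-relapsers | 68.5% | 40.6% | 1.69 |
| Planned rates, plus 20% of non-relapsers | 72.0% | 47.2% | 1.53 |
| Planned rates, plus 30% of non-relapsers | 75.5% | 53.8% | 1.40 |
| Equal in both arms | 45% | 45% | 1.00 |

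**Delta carried only through the regression.** Placebo subjects relapse earlier, so their delta passes through more visits and carry-through is not equal. Passing delta along the eight visits (assumed compound-symmetry or autoregressive correlation of 0.5 to 0.9) gives 1.73 to 1.94 with no other dropout and 1.25 to 1.71 with 10 to 30% other dropout.

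**SE allowed to grow with delta.** With assumed effects of 4 to 7 points, SD 6 to 7 and 49 per arm, the gap is 1.59 to 1.83 at 65%/34% and 0.88 to 0.98 at equal missingness. For example, with an effect of 5, SD 7 and 65%/34% missing, the tipping delta1 is 6.21 at delta2 = 0 and 4.45 at delta2 = 1, a gap of 1.76. In whole-number steps, significance is lost at 7 rather than at 5.

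**The case against.** The strongest reply is that the grid does what the SAP sets out to do. The stated aim is two-sided, with ecopipam dropouts made worse while placebo dropouts are made better, and no ecopipam-only tipping point is promised. The other two analyses also cover part of the ground. MAR imputation supplies roughly (0,0), and jump to reference is an ecopipam-worsened scenario with no placebo reward. Finally, leaving out delta2 = 0 can only make ecopipam look less robust, so it cannot prop up a false claim of efficacy.

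All of this stands as a limit on importance. A reader might infer that no scenario without a placebo reward is run at all; jump to reference shows otherwise. It is, however, a single fixed scenario that is not indexed by delta, so it yields no tipping value. The delta-indexed one-arm row is still absent, and the boundary near the origin still cannot be located.

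**Conclusion.** The structural point is certain: text and code agree, and no combination has a zero delta. Its size is not certain. Roughly 1 to 2 points at delta2 = 1 is an assumption-based range, and the upper end requires the planned relapse rates with no other dropout.

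Three stronger readings are not supported.

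- A reader might take 2 points as a minimum. It lies near the top of the range. The highest value found, 2.08, needs one particular reading of the visit-assignment rule together with full, equal carry-through, a fixed SE and no other dropout.
- A reader might conclude that a significant result would in practice be lost at the first grid point. That depends on a difference and an SE that the documents do not give.
- A reader might take the primary analysis to be affected, since 10.2.25 speaks of the robustness of the primary efficacy analysis. The model concerned is the mean-change one, as Step 2 of 16.4 says. The log-rank primary has its own sensitivity analysis in 10.1.1.

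The effect is conservative and confined to exploratory mean-change endpoints. This is a worthwhile improvement at almost no cost, and not a threat to the trial's conclusion.

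**What to change.** Before unblinding, let delta1 and delta2 each start at 0 in item 3 of 10.2.25.1 and in the opening paragraph of 16.4, and change the Step 1 loops to `do i=0 to 10; do j=0 to 10;`. State that the delta2 = 0 row will be reported as the ecopipam-only tipping point, beside the two-way grid.

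The cost is a few characters of text and code and 21 more combinations (121 instead of 100). At 100 imputations each, that is 12,100 imputed datasets instead of 10,000. No planned scenario is lost. The new (0,0) cell also gives a check on the programming: it should come close to the MAR analysis, though not match it exactly, because 16.2 and 16.4 use different imputation steps.

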# 11. Pharmacokinetics

Blood samples will be collected to measure concentrations of ecopipam and its major (active) metabolites at Weeks 4 and 8 or Week 12 if the 8 PK assessment is missed, during the open-label Stabilization period.

For the Week 4 visit, subjects and parents/caregivers (as applicable) will be instructed to skip the study medication on the evening prior to the Week 4 visit and to record the date and time that their last dose of study medication was taken. The study drug administration will occur on the day of the Week 4 visit at the site under the supervision of the study investigator. An intravenous catheter will be placed, and the subject will have samples collected at the following time windows: one sample at predose (34 to 44 hours since the last dose), one sample between 0.5 and 1.5 hours after administration of study medication, and one sample between 2 and 4 hours after study drug administration. Any samples should be collected at least 30 min apart.

For the Weeks 8 or 12 visit, subjects and parents/caregivers (as applicable) will be asked to record the date and time that their last dose of study drug administration was taken. A blood sample for PK will be collected. The time of sample collection will be recorded. Blood samples will be processed as outlined in the laboratory manual and analyzed for concentration of ecopipam and its major metabolite N - desmethylecopipam (EBS-101-40853).

To characterize the pharmacokinetics (PK) of ecopipam in all subjects: Plasma concentration-time data will be summarized in the Clinical Study Report (CSR). Population pharmacokinetic and pharmacodynamic analyses will be conducted and summarized separately, using data from this study along with data from other studies. The methodology for analyses will be reported in a separate analysis plan.

# 12. Safety

The population used for safety analyses will be the Safety Set (SS). Safety will be assessed by monitoring and recording all adverse events (AEs) and Serious Adverse Events (SAEs) (all Visits), regular monitoring of hematology, blood chemistry, and urine values (Screening, Baseline, Week 12, Week 18 and Week 24 Completion or Relapse/Early Termination, and 7- and 14-day Follow Up visits). HbA1c will be measured at Baseline, Week 12 and at Week 24 Completion or Early Termination visits. Regular measurement of vital signs and the performance of a physical examination will occur at every visit. An ECG will be performed at Screening, Baseline and Weeks 4, 12, 18, and 24 after supine BP is collected and at the 7-day and 14-day Follow Up visits. An additional assessment will include the Columbia-Suicide Severity Rating Scale (C-SSRS) (all Visits except 30 day Follow up visit). The Screening/Baseline version will be administered at Screening and the Since Last Visit version of the scale will be administered at all subsequent visits. Additional safety outcomes (Baseline and Weeks 4, 8, 12, 13, 14, 15, 16, 18, 20, 22 and 24) will include the Children's Depression Rating Scale-Revised (CDRS-R), the Pediatric Anxiety Rating Scale (PARS), the Extrapyramidal Symptom Rating Scale (ESRS), the Swanson, Nolan, and Pelham (SNAP-IV-26) questionnaire, the Children's Yale-Brown Obsessive Compulsive Scale-II (CY-BOCS-II), the Patient Health Questionnaire-9 (PHQ-9), the Hamilton Rating Scale for Anxiety (HAM-A), the Conners' Adult ADHD Rating Scale (CAARS) and the Yale-Brown Obsessive-Compulsive Scale-II (Y-BOCS-II). The C-SSRS and ESRS will be administered to all age groups whereas PARS, SNAP-IV-26, CY-BOCS-II and CDRS-R will be applicable for only children and adolescent subjects. The Y-BOCS-II, PHQ-9, CAARS and HAM-A will be administered to only adult subjects (>=18 years of age).

All safety data will be summarized using the Safety Set according to the actual treatment.

Treatment-emergent adverse events (TEAEs) are defined as adverse events that are newly occurring or worsening after the first dose of study medication. The incidence of TEAEs will be summarized by treatment group, by severity and by relationship to study medication. Serious TEAEs and TEAEs leading to the study termination will be summarized by treatment group. Laboratory data, vital sign, physical examination, and ECG will be summarized by treatment and visit.

Timing-specific adverse events are defined as any adverse events that occur or increase in intensity during any specifically defined study milestones: Up-titration (Week 1-4), open-label maintenance (Weeks 5-12), double-blind R/WD (Weeks 13-16), double-blind R/WD (Weeks 17-24), Down-titration (Post Week 24 or early termination) The incidence of Up-titration and open-label maintenance phase AEs will be summarized for Ecopipam and double-blind R/WD and Down-titration AEs will be summarized by treatment group, by severity and by relationship to study medication and will be displayed such that comparisons can be made. The C-SSRS, CDRS-R, PARS, ESRS, SNAP-IV-26 questionnaire, CY-BOCS-II, PHQ-9, HAM-A, CAARS and Y-BOCS-II will also be summarized descriptively.

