# 12.1. Adverse Events / Adverse Drug Reactions

An adverse event (AE) is any untoward medical condition that occurs in a patient while participating in this clinical study. Adverse events will be coded according to the Medical Dictionary for Regulatory Activities (MedDRA 25.0 or later) terminology and the severity of the toxicities will be graded according to the National Cancer Institute (NCI) Common Toxicity Criteria for Adverse Events (CTCAE), v4.03, where applicable. An adverse drug reaction (ADR) means any AE caused by a drug or biologic.

This document is confidential.

SAP text Version: SAP text 3.0 6-Dec-2023

Controlled Document ID: 3903A.02, Effective Date 31-Aug-2020

A Clinical Adjudication Committee (CAC) will review selected treatment emergent neurological adverse events that are known to occur as the result of dopamine receptor antagonists (see Appendix 16.5). The details of the CAC procedures and adjudication process will be reported in a CAC charter.

Treatment-Emergent Adverse Events (TEAEs) are those adverse events/adverse drug reactions that are recorded during or following the initiation of study treatment administration, and do not necessarily have a causal relationship to the use of the study medication. Treatment-Emergent Adverse Events (simply referred to as adverse events in summary tables) will be summarized.

The following adverse event summary tables will be summarized by treatment group:

- An overall summary with the number and percentage of patients reporting AEs, serious AEs
  (SAEs), maximum severity AEs, treatment-related AEs, treatment related SAEs, AEs leading to
  study treatment discontinuation and AEs with outcome of deaths.
- 2) AEs overall and by system organ class and preferred term.

In this summary, a patient is counted once at the system organ class and once at each preferred term within the system organ class.

- AEs overall and by system organ class, preferred term and initial daily dose level.
- 4) AEs overall and by system organ class, preferred term and region.
- 5) AEs overall and by system organ class, preferred term and weight band.
- 6) AEs overall and by system organ class, preferred term and time within the titration phase of open-label stabilization period. In all summaries by time the time windows are based on time since fist dose of ecopipam and will be as follows: 1-7, 8-14, 15-21, 22-28, 29-56, 57-84, 85-91, 92-98, 99-105, 106-112, 113-126, 127-140, 141-154, 155-168, 169-175, 176-184.

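### The adverse event displays specific to the randomized-withdrawal (R/WD) period compare arms by crude percentages, although the plan expects Relapse to cut placebo time at risk more; person-time rates should be added

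*SAP*

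**What the plan says.** SAP section 12 defines timing-specific adverse events by milestone and splits R/WD into Weeks 13-16 and Weeks 17-24. It states that "double-blind R/WD and Down-titration AEs will be summarized by treatment group", by severity and relationship, and laid out to permit comparison. Two tables in the numbered list of SAP 12.1 are specific to this period: item 8 (events by time within R/WD) and item 15 (events by milestone).

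The overall summary in SAP 12.1 is the "number and percentage of patients reporting AEs". In the term-level tables a patient counts once per system organ class and once per preferred term. SAP 8.1 summarizes categorical variables as counts and percentages of subjects. No denominator is stated for the time windows.

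Under SAP 4.1 a subject who meets Relapse criteria "will be withdrawn from blinded study medication (ecopipam or placebo"). SAP 4.3 assumes that the proportions who relapse are "65% in the placebo group and 34% in the ecopipam group".

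SAP 9.5 summarizes duration of exposure by period and treatment group, but no adverse event table uses it. Neither protocol 13.4.2 nor the SAP specifies a person-time rate or a time-to-first-event analysis for adverse events. Protocol 12.2.1.1 counts worsening of TD as an adverse event.

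**The concern.** R/WD is the trial's only randomized safety comparison, and safety and tolerability is a secondary objective. If ecopipam works as assumed, its subjects stay on blinded drug longer and have more time in which to record an event. A percentage of subjects ignores this. Equal underlying event rates would then appear as more events on ecopipam, most visibly in the later window. Events with onset after early termination fall into the separate Down-titration milestone, so the R/WD columns stop when a relapsing subject stops. At stake is how the R/WD adverse event tables are read, including events of special interest such as weight gain, extrapyramidal reactions and suicidality if these are tabulated by onset in R/WD.

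**Working it through.** **Inputs.** From SAP 4.3: Relapse in 65% of placebo and 34% of ecopipam subjects, hazard ratio 0.4, two-sided alpha 0.05, 85% power, 49 events and 98 randomized subjects. From SAP 4.4: 1:1 allocation and a 12-week R/WD period.

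**The plan's own figures reproduce.** The plan says "The planned number of Relapse events for the double-blind R/WD Phase is 49 in children and adolescents", and of power "This number of events will provide 85% power to detect a difference between treatment groups".
- Freedman's formula: (1.960 + 1.036)² × (1.4/0.6)² = 8.98 × 5.44 = 48.9, so 49 events. Power at 49 events: Φ(7 × 0.6/1.4 − 1.960) = Φ(1.04) = 85.1%.
- Expected events from 49 per arm: 49 × 0.65 + 49 × 0.34 = 48.5.
- Hazard ratio implied by the two proportions: ln(0.66)/ln(0.35) = 0.396.

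The Relapse proportions are therefore consistent with the rest of the design.

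**Time on blinded drug.** Assume a constant Relapse hazard λ = −ln(1 − p)/12 per week and no other dropout.
- Placebo: λ = 0.0875; mean time = 0.65/0.0875 = 7.43 weeks.
- Ecopipam: λ = 0.0346; mean time = 0.34/0.0346 = 9.82 weeks.
- Ratio 1.32. With 49 per arm this is 364 and 481 subject-weeks.
- Weeks 17-24, per randomized subject: (S(4) − S(12))/λ = 4.05 and 6.08 weeks, ratio 1.50.
- Still at risk at Week 16: 70.5% and 87.1%.

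**Crude incidence with the same adverse event hazard m in both arms.** P = m/(m + λ) × (1 − exp(−12(m + λ))). Here m is set by the risk over a full 12 weeks, m = −ln(1 − risk)/12. These risks are illustrative; the documents give none.

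| Full 12-week risk | Placebo | Ecopipam | Ratio |
|---|---|---|---|
| 10% | 6.2% | 8.2% | 1.31 |
| 30% | 19.1% | 24.9% | 1.30 |
| 50% | 32.8% | 41.9% | 1.28 |

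Mean time to the first of event, Relapse or Week 12 is (1 − exp(−12(m + λ)))/(m + λ). Dividing P by it returns m in both arms, so the person-time rate ratio is 1.00.

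**By window, 30% case.**
- Weeks 13-16, all randomized: 9.5% vs 10.5%, ratio 1.10.
- Weeks 17-24, all randomized: 10.9% vs 16.2%, ratio 1.49.
- Weeks 17-24, those at risk at Week 16: 15.4% vs 18.6%, ratio 1.20.

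An at-risk denominator alone is not enough, because placebo subjects keep leaving within the window.

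**Sensitivity of the exposure ratio.**
- Relapse dated at scheduled visits: 7.94 vs 10.10 weeks, 1.27.
- Mean time to Relapse t, the same in both arms: (0.34t + 7.92)/(0.65t + 4.20), which is 1.56 at t = 2 weeks and 1.13 at t = 8 weeks.
- Adding 30 days (4.3 weeks) of follow-up: 14.12/11.73 = 1.20.
- Adding the 12 open-label weeks as well: 26.12/23.73 = 1.10.

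**If a share q of Relapses is also recorded as an adverse event.** P(any AE) = (m + qλ)/(m + λ) × (1 − exp(−12(m + λ))). In the 30% case (placebo vs ecopipam):
- q = 10%: 24.8% vs 27.7%.
- q = 25%: 33.2% vs 32.1%.
- q = 50%: 47.3% vs 39.3%.

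The crossover depends on the background risk. In the 50% case, q = 25% still gives 45.2% vs 48.2%.

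**The case against.** The strongest objection concerns scope. A reader might infer that every adverse event, SAE, special-interest and discontinuation table carries a bias of about 1.3. The documents do not support that. Only the section 12 display and items 8 and 15 of SAP 12.1 are R/WD-specific. The other tables cover treatment-emergent events from Day 1 with no stated end cut, and events are collected to 30 days after treatment. Their exposure ratio is about 1.1.

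A reader might also infer that any-AE and SAE totals must show an ecopipam excess. That does not follow either. Worsening of TD is an adverse event. Hospitalization for it is both a Relapse criterion and a seriousness criterion, so Relapse itself generates events, mostly on placebo. This can cancel or reverse the any-AE difference. It is a second distortion of the total and does not correct the percentages for events unrelated to tics.

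The Weeks 17-24 ratio of 1.5 assumes an all-randomized denominator, on which the SAP is silent.

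The SAP is not blind to time. Narrow windows and the exposure summary let a reader see part of the imbalance, but no adverse event rate uses either.

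Finally, safety is descriptive, with no between-arm test or decision rule. In the 30% case with 49 per arm, the artefact is about 9 vs 12 subjects: 0.057/√(0.191 × 0.809/49 + 0.249 × 0.751/49) = 0.7 standard errors. That limits the consequence but leaves the measure biased.

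**Conclusion.** The point holds for the R/WD-specific displays. On the plan's own Relapse assumptions, ecopipam has about 1.3 times the placebo time on blinded drug. A non-tic adverse event with equal hazards then shows a crude risk ratio of about 1.3 over R/WD. In Weeks 17-24 the ratio is about 1.5 or 1.2, depending on the unstated denominator. The result assumes constant Relapse and event hazards, event timing independent of Relapse, no other dropout, and adults who relapse like the children and adolescents to whom the 65% and 34% apply. The size moves with these assumptions, but the exposure ratio stayed above 1 in every scenario tried. No direction is claimed for any-AE or SAE totals. This should be corrected before unblinding, but it does not invalidate the safety analysis.

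**What to change.** In SAP 12 and 12.1, for adverse events, SAEs, events of special interest and events leading to discontinuation with onset in R/WD:

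- Add subjects with a first event per 100 subject-weeks at risk, by arm, with the rate difference and 95% CI. Count time from the first post-randomization dose to the event or the last blinded dose, ending before the down-taper so that it matches the SAP's separate Down-titration milestone.
- Give this overall and for Weeks 13-16 and Weeks 17-24, beside the crude percentages.
- State the number at risk at the start of each window.
- Show the totals with and without TD-worsening events.

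This should not extend to laboratory and ECG findings. SAP 12.2 plans by-visit summaries and shift tables with no laboratory outlier counts. ECG outliers (SAP 12.4) are mainly found at scheduled visits, where subject-weeks at risk fit poorly.

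The cost is SAP wording and a few table columns, from dose and onset dates already collected. A single rate assumes a roughly constant hazard. Splitting by window only partly relaxes that, because placebo subjects are still tapering off ecopipam early in R/WD.
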